## 2.2 Background

CLTX-305 (encaleret) (known previously as JTT-305 or MK-5442), is an oral calciumsensing receptor (CaSR) antagonist (calcilytic), originally developed for the treatment of osteoporosis, that is now being evaluated as a potential treatment for autosomal dominant hypocalcemia type 1 (ADH1) in this dose finding proof-of-concept trial.

Previously, CLTX-305 (encaleret) was developed as a treatment for osteoporosis by Japan Tobacco Inc., (JTI) and Merck, Sharp & Dohme Corp., (Merck); Healthy volunteers and postmenopausal women with osteoporosis participated in a 1,766-participant program of which 1,280 were exposed to CLTX-305 (encaleret) in eight phase 1 and four phase 2 studies including exposures up to 52 weeks. Despite early data demonstrating a potential net benefit on bone formation, late phase trials failed to demonstrate efficacy on endpoints of bone mineral density (BMD) in postmenopausal women with osteoporosis.

Hypercalcemia was identified as an on-target but dose-limiting side effect in the osteoporosis program as reviewed below. Hypercalcemia was a safety issue in the osteoporosis program, whereas it is considered a marker for efficacy in the ADH1 program. The goal of the current program is to develop CLTX-305 (encaleret) as a targeted therapy to treat hypocalcemia and disturbed calcium homeostasis in patients with chronic hypocalcemia due to activating mutations in the calcium sensing receptor (CaSR).

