#### 2.2.2 Efficacy of CLTX-305 (encaleret) in Prior Clinical Trials

During the prior development program in osteoporosis, dose-related increases of endogenous serum parathyroid hormone (PTH) and calcium (Ca) were observed in participants with presumed normal CaSR function (i.e., healthy volunteers and postmenopausal women with osteoporosis). In healthy postmenopausal women, repeat CLTX-305 (encaleret) doses of 15 or 20 mg resulted in consistent elevations in intact PTH (iPTH) over 3-4 hours post single daily dosing. The stimulatory effect on iPTH was consistent, without evidence for tachyphylaxis, after 6 and 12 months of once daily administration. CLTX-305 (encaleret) dosing in phase 2 studies was limited to 15 mg once daily (QD) to minimize hypercalcemia.

With chronic once-daily dosing up to 15 mg, albumin-corrected blood calcium (cCa) levels reached a plateau with up to 30% of participants registering an elevated blood calcium above the upper limit of the laboratory reference range during long-term trials in postmenopausal women with normal systemic calcium homeostasis (normal CaSR sensitivity). Such hypercalcemia was asymptomatic, modifiable by decreasing calcium/vitamin D supplementation, and/or resolved after stopping CLTX-305 (encaleret) dosing. No serious adverse events (SAEs) related to either hyper- or hypocalcemia were observed in the CLTX-305 (encaleret) program for osteoporosis in postmenopausal women (See IB Section 5.2).

In summary, extensive data from the prior osteoporosis development program demonstrated that CLTX-305 (encaleret) is associated with dose-proportional increases in peak serum iPTH levels in participants presumably expressing wild-type *CaSR*, with iPTH elevations lasting less than 8-12 hours but associated with elevations in cCa at chronic daily oral doses of 15 mg or above.

## 2.2.3 Autosomal Dominant Hypocalcemia, Type 1

ADH1 is a rare disorder of systemic calcium homeostasis caused by activating mutations of the CaSR gene leading to hypocalcemia (Hannan 2012, Hofer 2003). The CaSR plays the dominant role in regulating systemic calcium homeostasis by controlling PTH secretion and urinary calcium excretion in response to variations in blood calcium levels (Hofer 2003,

1100001. CB111 300 201 1 michanical 10. 10 may 2020 1 mi 20 B 0122

Gunn 2004). Negative allosteric modulators of the CaSR, (so-called calcilytic agents) may represent a potential targeted therapy for ADH1.

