In the prior osteoporosis program, hypercalcemia adverse events were not symptomatic and were identified based on scheduled periodic laboratory assessments. Dose-limiting thresholds for post- CLTX-305 (encaleret) cCa levels are specified as part of the dosing and titration algorithms in Section 8.2. In Summary, participants who achieve a post-dose cCa > 10-10.5 mg/dL (in Period 1) and cCa > 10 mg/dL (in Period 2) during the dose escalation will not proceed to higher CLTX-305 (encaleret) doses. Participants with cCa values between 10-10.5 mg/dL during dose escalation in Period 1, will have their doses increased by 30 mg only. Participants who achieve cCa > 10-10.5 mg/dL in Period 1 and >10 mg/dL in Period 2 will have their dose maintained or reduced and undergo final frequent sampling as appropriate.

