The investigator or qualified sub-investigator will review all laboratory results for clinical significance. Any laboratory result deemed clinically significant (i.e., is associated with signs and symptoms and/or requires medical intervention) will be recorded as an AE as described in Section 8.5.5.

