## 8.5.7 Events of Special Interest

#### Hypocalcemia in ADH1

The main goal of CLTX-305 (encaleret) treatment in participants with ADH1 is to raise serum calcium levels. Hypocalcemia is not an expected side-effect of treatment with CLTX-305 (encaleret) but it is a complication of the underlying disease being treated. As such, hypocalcemia may develop whenever the underlying disease is inadequately treated and might occur due to either inadequate or missed doses of a specific, effective medication.

The current study involves reducing the dose of current maintenance medications or suspending their use entirely (i.e., oral calcium supplements and calcitriol), to facilitate dose-finding with the CLTX-305 (encaleret) and potentially establishing clinical proof-of-concept. Under these circumstances there is a risk that participants could experience symptoms of hypocalcemia prior to achieving an effective dose of CLTX-305 (encaleret). In order to mitigate this risk, the study design emphasizes safety foremost. All changes to oral maintenance medications in conjunction with CLTX-305 (encaleret) dosing will be conducted with participants in residence at the NIH Clinical Center in the first two periods, with multiple daily measurements of blood calcium and close supervision by health professionals with experience caring for individuals with ADH1. In addition to these precautions, monitoring for and capture of events suggestive of or consistent with hypocalcemia will be reviewed as an AE of special interest as described below.

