# 9.6 Safety Analyses

Safety and tolerability parameters will be summarized using descriptive statistics, where appropriate. All safety data will be provided in data listings.

AEs will be coded using the MedDRA dictionary. The incidence of each treatment-emergent AE (TEAE) will be summarized by system organ class, preferred term and treatment assignment. Multiple AEs mapped to the same preferred term will be counted once per participant. Concomitant medications will be coded using the WHO Drug Dictionary with generic term and Anatomical Therapeutic Chemical (ATC) code and summarized by ATC code, WHO Drug generic name, and treatment. Reasons for early termination will be summarized by treatment group assignment. Safety laboratory findings, vital signs, and 12-lead ECGs will be summarized descriptively and listed by treatment assignment and visit. Values and changes from baseline at scheduled time points will be summarized. Laboratory data will be listed and values and changes from baseline at each visit will be summarized. An additional listing of treatment-emergent laboratory abnormalities will be provided.

An AE (classified by preferred term) that occurs during the treatment period will be considered a TEAE if it was not present before the first dose of CLTX-305 (encaleret) or if it was present before the first dose of CLTX-305 (encaleret) but increased in severity during the treatment period. If more than 1 AE is reported before the first dose of CLTX-305 (encaleret) and is coded to the same preferred term, the AE with the greatest severity will be used as the benchmark for comparison with the AEs that were also coded to that preferred term and that occurred during the period. An AE that occurs more than  $30 \pm 7$  days after the last dose of CLTX-305 (encaleret) will not be counted as a TEAE.

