Adverse events of special interest will be presented separately by Periods. The number and percentage of subjects with hypocalcemia (symptomatic and/or asymptomatic) as well as number and percentage of subjects for each symptom for symptomatic hypocalcemia will be presented.

All adverse events (including non-treatment-emergent events) recorded on the CRF will be listed.

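### SAP 13.6 plans no participant count of raised calcium or low phosphorus, and the protocol's listing of laboratory abnormalities is not carried over

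*SAP*

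**What the plan says.** **The effect.** Protocol 2.2 states: "Hypercalcemia was identified as an on-target but dose-limiting side effect in the osteoporosis program". Protocol 6.1.7 adds that it was the only signal that forced a cap on chronic doses. Protocol 2.3.1 names hypophosphataemia as a further possible fluctuation, and 8.2.2 titrates to keep phosphorus above the lower limit of normal.

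**The limits.** Protocol 6.1.7 and 6.1.8 restrict escalation at cCa of 10 to 10.5 mg/dL in Period 1 and above 10 mg/dL in Period 2, and call for dose modification above 10 mg/dL in Period 3 and the LTE. Protocol 8.2.3 lets investigators consider a hold above 10.5 mg/dL in Period 3.

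**When a laboratory value becomes an AE.** Protocol 8.4.3 has two sentences. One covers clinically relevant abnormalities and gives dose interruption, symptoms or signs, and therapeutic intervention as examples. The other reads: "Any laboratory result deemed clinically significant (i.e., is associated with signs and symptoms and/or requires medical intervention) will be recorded as an AE".

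**The safety outputs.** Protocol 9.6 promises: "An additional listing of treatment-emergent laboratory abnormalities will be provided". SAP 13.6.1 tabulates TEAEs by SOC and preferred term. Its special-interest table gives "The number and percentage of subjects with hypocalcemia (symptomatic and/or asymptomatic) as well as number and percentage of subjects" for each symptom of hypocalcaemia. SAP 13.6.3 gives values and changes from baseline for the Table 5 analytes, which do not include calcium, cCa or phosphorus. For Periods 1 and 2 it summarises only creatine kinase and potassium.

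**Where calcium and phosphorus go.** SAP 13.7.1 and 13.7.2 report cCa and phosphorus under efficacy/PD. SAP 13.0 sets the statistics (n, mean, SD, median, quartiles, minimum, maximum) and lists all collected data.

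**The concern.** A safety table should answer how many participants exceeded the limits at which the protocol restricts dosing. Descriptive statistics do not answer that. A mean can sit in range while individuals are above it, and a maximum at each timepoint does not show whether high values belong to one participant or to several. Protocol 4.3 expects doses that cause hypercalcaemia to mark the upper bound of dosing, which makes the participant count useful for dose characterisation as well as for safety.

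The AE route is the only one in the visible safety section that yields a count, and it depends on the investigator's judgement for the kind of case seen before: a raised value found on a scheduled test in a participant who feels well. The listing in protocol 9.6 would have been the natural backstop.

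**Working it through.** The documents state no figure to reproduce. The check follows each type of event through the recording rules to the planned tables.

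| Event | Does the protocol lead to an AE? | Counted in SAP 13.6? |
|---|---|---|
| cCa below 7 mg/dL, no symptoms | Yes, by threshold (8.5.7) | Yes, special-interest table |
| High cCa with symptoms or treatment | Yes (8.4.3) | Yes, TEAE by preferred term |
| High cCa, no symptoms, dose held | Yes, fits the dose-interruption example (8.4.3) | Yes, TEAE by preferred term |
| High cCa, no symptoms, dose maintained or lowered without a hold | Not named; left to judgement | Only if recorded |

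The low side has a numerical trigger for an event and the high side has none. Protocol 6.1.8 does not close the gap. Its instruction to capture abnormalities as AEs concerns those unrelated to the dosing algorithm, and it gives corrected calcium as an example of an algorithm parameter.

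**Placement.** The protocol's own safety panels (footnotes to Tables A to D) include calcium and phosphate. SAP Table 5 does not.

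**The listing.** It appears in protocol 9.6. It is not in SAP 13.6.3, and it is not among the changes declared in SAP 6.1.

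**Scale.** The synopsis allows up to 16 treated participants.

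- One uncounted participant: 1/16 = 6.25 percentage points.
- A table showing 0 of 16: two-sided 95% Clopper-Pearson upper limit = 1 − 0.025^(1/16) = 20.6%.
- A table showing 1 of 16: 95% limits 0.2% to 30.2%.

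**A tempting projection.** Protocol 2.2.2 reports "up to 30% of participants registering an elevated blood calcium above the upper limit" of the reference range. Applied here, that gives 0.30 × 16 = 4.8 participants, and P(at least one) = 1 − 0.70^16 = 0.997. This is arithmetic on an assumption, not an estimate for this trial. The figure is the top of a range, seen in postmenopausal women with normal receptor function on once-daily doses up to 15 mg. Here the receptor is altered, doses are higher and individually titrated, and Period 2 aims to keep cCa below 10 mg/dL. The measure is also different: a reference limit there, dosing limits here.

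**The case against.** The strongest reply is that the protocol deliberately classifies the finding. Sections 2.2 and 6.1.7 treat a calcium rise in ADH1 as evidence of effect rather than harm, so reporting it under efficacy/PD is a design decision. Section 8.5.7 likewise justifies hypocalcaemia as the event of special interest, because calcium and calcitriol are cut back or stopped. Both points stand as reasons for the placement. Neither covers values beyond the limits at which the same protocol restricts or modifies dosing.

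Several stronger readings should be set aside.

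- *High values would be invisible.* They would not. Minimum and maximum are tabulated, SAP 13.7.1 adds individual cCa plots in Period 3, and all data are listed. What is missing is the participant count in the safety section.
- *Asymptomatic cases will not become AEs.* This does not follow. In the earlier programme "hypercalcemia adverse events were not symptomatic and were identified based on scheduled periodic laboratory assessments", so such cases were recorded as AEs there. The wider sentence in protocol 8.4.3 gives examples only, so an investigator may record a dose reduction.
- *The listing was deliberately dropped.* The SAP is silent. It is to be read with the protocol (SAP 6.0), and changes from protocol-planned analyses are to be documented in the CSR (SAP 4.0).
- *No categorical cCa table exists anywhere.* This cannot be said. SAP 13.7.3 is not in the available text, and the change history mentions responder endpoints for cCa. Such a table would be an efficacy output, and the visible 13.6 has no equivalent.

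**Conclusion.** The point holds as a gap in safety reporting. In visible SAP 13.6 no output counts participants with raised cCa or low phosphorus unless an AE is recorded, and the protocol 9.6 listing is neither carried over nor declared omitted. Asymptomatic exceedances managed by down-titration may therefore go uncounted in the primary safety tables.

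A reader might infer that about 5 of 16 participants would exceed the limit while the AE table shows 0 of 16. The documents support neither number: the earlier rate does not transfer, and the recording rule permits such events to be entered. The number uncounted is unknown and may be zero.

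The conclusion rests on two assumptions: that SAP text not available here contains no equivalent safety count, and that investigators keep some discretion over recording a dose reduction. It does not depend on any assumed rate. This is a cheap improvement, and the primary efficacy analysis is unaffected.

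**What to change.** In SAP 13.6.3:

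1. Add the number and percentage of participants, by period and visit, with any post-dose cCa above the laboratory upper limit, above 10.0 mg/dL and above 10.5 mg/dL, and with phosphorus below the lower limit of normal, whether or not an AE was recorded.
2. Carry over the listing of treatment-emergent laboratory abnormalities from protocol 9.6.

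Show the number of post-dose samples beside each percentage, because the chance of any exceedance rises with sampling. Protocol Table H has nine post-dose calcium samples a day in Period 1 (Days 1 to 3), whereas NIH visits in the LTE take laboratory samples about 4 hours after the morning dose.

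The cost is one table and one listing from data already collected. The safety figures may look slightly less favourable. The cut-offs are the laboratory's and the protocol's own, so no dosing rule or clinical threshold is changed or endorsed.

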13.6.2 Deaths and Serious Adverse Events

Serious TEAEs and serious TEAEs related to study treatment will be summarized by SOC and PT for each Period and overall.

13.6.3 Laboratory Data

Safety Laboratory data (hematology and chemistry) will be presented using SI units and tabulated by dose, day and time-point (where applicable) for Period 1; by day and time-point (where applicable) for Period 2, and by analysis visit and time-point (where applicable) for Period 3 and by analysis visit for LTE.

Absolute values and change from baseline will be summarized. Creatine Kinase and Potassium will be summarized by time-points. The mean \pm SD of creatine kinase concentrations and the mean \pm SD of potassium concentrations at each visit and timepoint (where applicable) during each period will be graphically represented. In addition, spaghetti plots of the creatine kinase concentrations and potassium concentrations will be provided by visits and timepoints (where applicable) during each period.

Blood and urine samples for clinical laboratory tests will be collected at the times detailed in the Schedule of Activities in the protocol. At Screening (Period 1), the samples will be collected at the NIH Clinical Center. Additional testing during the Screening period or for Screening Period 2 (cohort 1 subjects) may be conducted at a local laboratory near the subject. All laboratory tests during the Treatment Periods 1 and 2 (days 1 to 5) and Weeks 8, 16 and 24 for Period 3 as well as Months 6, 12, 18 and 24 for LTE will be measured at the NIH Clinical Center. At other visits and per the schedule of events, local laboratory collection of blood and urine will be performed.

The clinical laboratory tests listed in Table 5 will be included in the safety summary tables. Creatine Kinase and Potassium will be summarized for all periods; the other parameters will be summarized for Period 3 and LTE only. Urinalysis results will be listed.

Hematology	Hemoglobin, hematocrit, complete blood count including red cell count and indices, white blood cell count, platelet count, and differential. Coagulation tests (PT, PTT, INR).
Blood Chemistry	Electrolytes (sodium, potassium, chloride), bicarbonate, glucose, blood urea nitrogen, alanine aminotransferase, aspartate aminotransferase, alkaline phosphatase, LDH, amylase, lipase, uric acid, creatine kinase, total protein, total bilirubin, 25-Hydroxy Vitamin D.

Table 5: Safety Laboratory Parameters

13.6.4 Vital Signs

Observed values and changes from baseline in vital signs will be summarized for each vital sign parameter by period and visit.

The summaries will include pulse rate, systolic blood pressure (SBP), diastolic blood pressure (DBP), respiratory rate, temperature, and weight. Pulse rate, SBP and DPB will be summarized by position for Period 1 and Period 2. For Period 3 and LTE, baseline will be defined for SBP, DBP and Heart Rate as the Period 2 Baseline using the supine position. All vital signs will be listed

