If participant discontinues from the study early (ET) or withdraws from taking CLTX-305 (encaleret) (EoT), perform related assessments, resume prior medication regimen, arrange FU labs within 1-2 days. Participants instructed to obtain outpatient laboratory testing (See Footnote 10) approximately 1-2 days after discharge from NIH CC. PI/Site

- staff should contact the participant within 3-5 days to review test results and provide guidance regarding clinical management as they transition to prior clinical care providers. Optionally, participants may stay in the NIH CC overnight to complete assessments.
-  Including CaSR mutational analysis (if not documented).
-  Safety Labs Chemistry (Na, K, Cl, bicarbonate, Glu, BUN, Cr, alb, total protein, Ca, Mg, PO4, iPTH, 25-OH Vitamin D, cholesterol, TG, AST, ALT, Tbili, Alk phos, LDH, amylase, lipase, uric acid), Hematology (RBC, Hgb, Hct, RBC indices, WBC, diff), Coagulation (PT/PTT/INR), urinalysis. HIV, viral hepatitis panel, and iron panel to be done at screening visit only unless repeat measures are clinically indicated.
-  Height measured at screening only.
- Vital signs include supine or sitting blood pressure (BP) by automated cuff, heart rate (HR), and respiratory rate, to be collected q8 hours during in-patient days. Orthostatic BP and HR will be assessed once at screening and once daily during Period 2.
- Discontinue calcitriol on Day -1 during the admission.
- Initial dose (Days 1 & 2) of CLTX-305 (encaleret) BID based on results from Period 1. If calcium has not increased into the normal range, then the CLTX-305 (encaleret) dose will be increased for Days 3-5. Participants will undergo frequent PK/PD sampling over 24h on Day 5.
-  24-hour urine at the screening visit 14 to 10 days prior to Day 1 dosing (Ca, Mg, PO4, Cr, Na, K, Citrate, pH)
- For cohorts 1 and 2: outpatient laboratory testing on days -14 to -10 before admission include: blood Cr, Ca, Alb, Mg, PO4, 25-OH Vitamin D, Hematology (RBC, Hgb, Hct, RBC indices, WBC)
- 11 Interval lab tests at outpatient laboratory will be done in those for whom the screening visit is >21 days prior to Period 2.
- After the last dose of CLTX-305 (encaleret), for participants continuing to Period 3, dispense supply of CLTX-305 (encaleret) before discharge.

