PD; Pharmacokinetic = PK; Procollagen type 1 N-propeptide = P1NP; Prothrombin Time/ Prothrombin Time = PT/INR; Red Blood Cell Count = RBC; Thromboplastin Time = PTT; Serious Adverse Event = SAE; QD = Once daily; Total Bilirubin = Tbili; Triglycerides = TGL; White Blood Count = WBC; Women Of Child Bearing Potential = WOCBP

- If participant discontinues from the study early (ET) or withdraws from taking CLTX-305 (encaleret) (EoT), before completing Period 3 per protocol, participant will be asked to return to the NIH CC as soon as possible for the ET/EoT visit assessments and return the unused CLTX-305 (encaleret). Participant should revert to their outpatient regimen of oral calcium and active vitamin D. Participants will go through FU activities as stated in table and footnote 2, and then will have a safety FU call 30 day ± 7 days.
- Participants who withdraw from taking CLTX-305 (encaleret) (EoT) before completing Period 3 per protocol or who elect not to continue into the LTE will obtain the following outpatient laboratory assessments after the last dose of CLTX-305 (encaleret) and after re-starting their prior regimen of oral calcium and active vitamin D: blood Cr, Ca, Alb, Mg, PO4. Follow-up (FU) call should occur within 3-5 days to review the lab results and receive guidance on clinical management of their ADH1 as they transition to their prior clinical care providers.
- Unscheduled visits: For laboratory evaluation following dose adjustment or assessment or follow-up of an AE, in which clinically indicated procedures will be performed.
- Document current CLTX-305 (encaleret) dose and calcium dosing regimen, any modifications, and reason for modifications.
- Outpatient laboratory testing: Blood samples for clinical laboratory panels (Na, Cl, bicarbonate, K, BUN, Cr and including Alb, Ca, Mg, PO4, iPTH, CTX and P1NP).
- 6 Height measured only at ET visit.
- Vital signs include supine or sitting blood pressure (BP) by automated cuff, heart rate (HR), and respiratory rate.
- Focused Physical exams: weight measurement at all visits.
- Safety Labs collected at the NIH CC visits—Chemistry (Na, K, Cl, bicarbonate, Glu, BUN, Cr, Alb, total protein, Ca, Mg, PO4, 25-OH Vitamin D, Cholesterol, TG, AST, ALT, Tbili, Alk phos, LDH, amylase, lipase, uric acid), Hematology (RBC, Hgb, Hct, RBC indices, WBC, diff), Coagulation (PT/PTT/INR).
- 10 CLTX-305 (encaleret) administered and recorded during the NIH CC visit/in-house PK/PD collection days.

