9.0 Study Endpoints, Variables and Covariates

Objectives	Endpoints							
Primary								
 Periods 1, 2, and 3: Evaluate the safety and tolerability of single and multiple doses of CLTX- 305 (encaleret) in subjects with ADH1. 	 Periods 1, 2 and 3: Number of subjects with adverse events (AEs), serious AEs Absolute values and change from baseline in clinical safety (laboratory tests), vital signs, and electrocardiograms (ECGs). AEs and serious AEs (SAEs) – frequency count and percentages of subjects; Clinical safety laboratory tests, vital signs and ECGs – absolute levels and change from baseline. 							
 Period 3: Evaluate the safety, tolerability and efficacy of CLTX-35 (encaleret) in subjects with ADH1 after 24 weeks. 	 Period 3: cCa after treatment with CLTX-305 for 24 weeks - absolute levels and change from baseline. Urinary calcium clearance (fractional excretion) after treatment with CLTX-305 for 24 weeks – absolute levels and change from baseline; Urinary calcium clearance (24-hour total excretion) after treatment with CLTX-305 for 24 weeks - absolute levels and change from baseline. 							
 LTE: Evaluate the longer-term safety and tolerability of CLTX-305 (encaleret) in subjects with ADH1 from Period 3 for approximately 25 months (approximately 2 years). 	 LTE: AEs and SAEs - frequency count and percentages of subjects; Clinical safety laboratory tests and vital signs for approximately 25 months (approximately 2 years) - absolute levels and change from baseline. 							
Secondary								
 Periods 1 and 2: Evaluate the effect of CLTX-305 (encaleret) to increase serum iPTH levels after both single and multiple doses across a dose range in subjects with ADH1. 	 Periods 1, 2, and 3: Absolute values and change from baseline in iPTH blood concentrations profiles (24-hours) over time after single and multiple doses of CLTX-305 (encaleret). 							

Objectives	Endpoints							
Secondary								
 Evaluate the PK of both single and multiple ascending doses of CLTX- 305 in subjects with ADH1 where intensive PK sampling was done. 	• PK parameters: maximum plasma concentration (C_{max}) , time to maximum plasma concentration (t_{max}) , apparent terminal half-life $(t_{\frac{1}{2}})$, area under the concentration-time curve (AUC) from time 0 to the last measurable time point (AUC _{0-t}), AUC from time 0 to 24 hours (AUC _{2-cu}) AUC							

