10.2 Change from Baseline

Change from baseline will be calculated as (value at post-baseline time point – value at baseline). Change from baseline will be calculated for subjects with both a baseline and post-baseline value as applicable. If a baseline or post-baseline value has not been recorded for a parameter, then change from baseline will not be calculated for that parameter. Subjects with missing change from baseline values will be excluded from descriptive statistics.

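### In Period 3 and the LTE, change in blood pressure and heart rate is taken from a supine-only baseline although visit readings need not be supine, so any sitting reading carries a posture difference

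*SAP*

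**What the plan says.** **Visit readings.** The vital-sign footnotes to Protocol 1.3 Table C (Period 3) and Table D (LTE) use the same words: "Vital signs include supine or sitting blood pressure (BP) by automated cuff, heart rate (HR), and respiratory rate". The SAP appendix repeats them in Tables 10 and 11. Vital signs are scheduled only at the NIH Clinical Center visits: Weeks 8, 16 and 24 in Period 3, and Months 6, 12, 18 and 24 in the LTE.

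**Baseline readings.** In Period 2, the source of the baseline, the routine readings are equally flexible: "Vital signs include supine or sitting blood pressure (BP) by automated cuff, heart rate (HR), and respiratory rate, to be collected q8 hours" on inpatient days. The same footnote to Table B adds: "Orthostatic BP and HR will be assessed once at screening and once daily during Period 2". The Period 3 and LTE footnotes ask for no orthostatic readings.

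**Analysis.** SAP 13.6.4 says: "Pulse rate, SBP and DPB will be summarized by position for Period 1 and Period 2". It then sets the later baseline: "For Period 3 and LTE, baseline will be defined for SBP, DBP and Heart Rate as the Period 2 Baseline using the supine position". SAP 10.2 gives the general formula, "Change from baseline will be calculated as (value at post-baseline time point – value at baseline"), and leaves participants without a change value out of the descriptive statistics.

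**Status.** SAP 9.0 lists among the primary endpoints for Periods 1 to 3: "Absolute values and change from baseline in clinical safety (laboratory tests), vital signs, and electrocardiograms (ECGs"). For the LTE it also lists vital signs, as absolute levels and change from baseline.

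**The concern.** The SAP treats posture as relevant. It separates positions in Periods 1 and 2, and it names a position for the later baseline. From Period 3 on, however, it controls posture on only one side of the subtraction. A sitting reading that complies fully with the protocol is set against a supine value and pooled with any supine readings from the same visit.

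The study is open-label with no control arm, so no concurrent group shares the posture shift and removes it. A mean change of a few units at Week 24 could then reflect the drug, the chair or both, and an offset of opposite sign could partly cancel a real change. This covers the longest exposure in the study: 24 weeks, then up to 25 months of LTE.

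A second, smaller gap concerns a participant with no supine reading before the first Period 2 dose. That participant has no baseline under 13.6.4 and drops out of the change summary, even where a sitting baseline and sitting visit readings both exist.

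**Working it through.** The plan states no figure on this point, so there is nothing to reproduce. The check sets the rules side by side and then shows what they imply.

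**Step 1: posture on each side of the subtraction**

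| Element | Posture rule | Source |
|---|---|---|
| Period 2 routine readings | BP supine or sitting; none stated for heart rate | Protocol Table B footnote |
| Baseline for Period 3 and LTE (SBP, DBP, heart rate) | Supine only | SAP 13.6.4 |
| Period 3 and LTE readings | BP supine or sitting; none stated for heart rate | Protocol Tables C and D; SAP Tables 10 and 11 |
| Change formula | No posture condition | SAP 10.2 |
| Summary by position | Periods 1 and 2 only | SAP 13.6.4 |

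Nothing in either document limits later readings to supine, matches their posture to baseline, or stratifies them.

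**Step 2: one reading.** Let *d* be the sitting-minus-supine offset for a participant. A sitting visit reading is the supine value at that visit plus *d*. Subtracting the supine baseline gives

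reported change = supine-to-supine change + *d*.

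**Step 3: the mean.** Let *f* be the share of readings at a visit taken sitting, with the same *d* for everyone (a simplification). Then

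bias in mean change = *f* × *d*.

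If the choice of posture is unrelated to the underlying change, mixing postures also adds a between-participant component with SD = |*d*| × √(*f*(1 − *f*)).

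**Step 4: illustration.** The documents give neither *f* nor *d*, so every value below is an assumption, in mmHg or beats per minute. Both signs are shown because the documents do not fix the direction.

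| Assumed *d* | *f* = 0 | *f* = 25% | *f* = 50% | *f* = 100% |
|---|---|---|---|---|
| −5 | 0 | −1.25 | −2.5 | −5 |
| −2 | 0 | −0.5 | −1 | −2 |
| +2 | 0 | 0.5 | 1 | 2 |
| +5 | 0 | 1.25 | 2.5 | 5 |
| +10 | 0 | 2.5 | 5 | 10 |

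For example, 0.50 × 5 = 2.5. For |*d*| = 5 the added SD is 5 × √(0.25 × 0.75) = 2.17 at *f* = 25%, 5 × √(0.5 × 0.5) = 2.5 at *f* = 50%, and 0 at *f* = 100%. With posture matched, or with supine readings only, both terms vanish.

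**Step 5: missing supine baseline.** SAP 10.1 takes the last non-missing value before the first dose in the period. Table B schedules vital signs at screening and on Day -1, and adds orthostatic readings at screening and daily. There are thus several chances of a supine value before dosing, although Cohort 1 participants are not re-screened for Period 2 and the protocol does not list the positions in an orthostatic assessment. SAP 10.1 also lets the Period 1 baseline stand in for Cohort 1 if nothing was assessed before the first Period 2 dose. It does not say whether a sitting-only record triggers that fallback, and Cohort 2 has none.

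**The case against.** The strongest reply is that the defect is conditional. If staff took every later reading supine, *f* = 0 and nothing is wrong. SAP 13.7.1 shows that this version was written after all participants had completed Week 24, so its authors may have known which positions were used. That is possible but cannot be confirmed: the case report form is not among the documents, and the supine wording in 13.6.4 applies to the baseline alone. If only supine readings were meant, the SAP should say so.

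A second reply is that little depends on the table. Protocol 9.1 calls for descriptive analysis, and the post-hoc t-tests in SAP 13.7.4 do not include vital signs. Absolute values are summarised beside the changes, every reading is listed, and Protocol 8.4.2 records clinically significant abnormal vital signs as adverse events whatever the change table shows. Respiratory rate, temperature and weight are untouched. All of this stands and keeps the severity low. It does not repair the change column, and the pooled absolute values also mix postures.

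Third, matching by position needs position to have been recorded after Period 2, and no text says that it was. This also stands, and the fix has to allow for it.

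A reader might infer more than the documents support: that the reported changes are in fact biased, by a particular amount or in a particular direction; that every Period 3 and LTE contact is affected; or that a participant whose last pre-dose reading was sitting has no usable baseline. The share sitting and the offset are not given, telephone contacts have no vital signs, and an earlier supine pre-dose reading can serve as baseline.

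**Conclusion.** The mismatch is real on the face of the two documents. For any sitting reading in Period 3 or the LTE, the stated rules produce a change in SBP, DBP or heart rate that includes a posture difference, in a measure listed as a primary safety endpoint and with no control arm to cancel it. Its size is *f* × *d*, with both factors and the sign unknown, and it is zero if all later readings were supine. The numbers in the table are illustrations, not estimates for this trial. Loss of a participant for want of a supine baseline is possible but less likely, given the screening, Day -1 and orthostatic readings. This is a low-severity correction: it affects how one descriptive safety table can be read and leaves the efficacy analyses untouched.

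**What to change.** Replace the baseline sentence in SAP 13.6.4 with:

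> For Period 3 and LTE, change in SBP, DBP and heart rate is calculated against the last pre-dose Period 2 value recorded in the same position as the visit reading, and is summarised by position; readings with no same-position baseline, or with no recorded position, are shown as absolute values only.

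First check whether the case report form captured position at the Period 3 and LTE visits. If it did not, footnote the change table to say that the change may include a posture difference.

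The cost is one sentence and one by-position layout, with no new data. The downside is smaller cells and some readings without a change value: with up to 16 participants treated, an even split would leave 16 × 0.5 = 8 per position.
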